6.1.3 EndoZip Electrical Power Supply (Reusable)

The EndoZip electrical power supply contains a unique and dedicated connector to the EndoZip disposable.

The EndoZip System complies with the IEC 60601-1 Ed. 3.1, 60601-1-6 Ed. 3.0 safety standards and IEC 60601-1-2 EMC standard.

	Title: Evaluation of EndoZip™ System (AS) in Obese Patients who failed to reduce weight with non-surgical weight-loss methods		
Document No: CL00003	Rev: 1.0	Page:	27 of 83

For detailed description of the device please refer to the current version of the study Investigator's Brochure (IB).

6.2 Pre-clinical data

Several bench tests were performed with the EndoZip™, to ensure that the device meets its design specifications and is safe for its intended use. Performance of the device was also evaluated, especially the mechanical properties, functional features and operational parameters.

NiTiNotes conducted animal studies during the first prototype development to evaluate the safety of the EndoZip system under in-vivo conditions. A swine model was chosen as it has been used extensively as a gastrointestinal model due to its anatomic and physiologic characteristics which are similar to humans. Notably, despite being the best model animal for human, the swine model may be very challenging and represents the worst-case scenario for this study as the swine's gastric capacity and surface tension are significantly greater compared with humans.

In this experiment, that included application of the system and suturing it was proven that the system is capable to perform approximation of the stomach tissue segments (Anterior and Posterior segments) and to suture said segments one to the other using a continuous suturing. Furthermore, EndoZip™ was considered non-irritant as expected in histological evaluation and a normal reaction to such a suture was observed in the procedure surroundings. Unexpected adverse reactions were not observed.

Although studies were performed on an earlier prototype device, the conclusion are valid to the final device as both configurations (i.e., prototype and final design) share similar suturing mechanism of action, meaning gripping and holding the tissue in the Bougie chamber using vacuum, and same needle, suture thread and clips' materials.

All components of the EndoZip™, that come in direct contact with the patient, were deemed biocompatible in accordance with the ISO 10993 biocompatibility standards.

For in-depth review of the pre-clinical investigations, please see the study Investigator's Brochure (IB).

6.3 Clinical data to Date

One clinical study has been conducted to date. The study was designed to evaluate the safety and the outcomes of the EndoZip prototype system with respect to obese patients' weight loss in 6 months. It was a single arm, prospective single center study, conducted by [name] at the Bariatric Endoscopy unit of HM Sanchinarro University Hospital, Madrid, Spain. The institutional review board approved the study. The study was conducted in accordance with the ethical principles detailed in the

	Title: Evaluation of EndoZip™ System (AS) in Obese Patients who failed to reduce weight with non-surgical weight-loss methods		
Document No: CL00003	Rev: 1.0	Page:	28 of 83

Declaration of Helsinki and was consistent with Good Clinical Practices recommendation (Clinicaltrials.gov, NCT03472196). The study results were published on January 2020 at Obesity Surgery Journal [OBES SURG (2020) 30:1696–1703].

Study Design - Patients in this study were instructed to be on a liquid diet and fast a day prior the procedure. BMI, waist circumference, blood tests and a Quality of life questionnaire were recorded prior the procedure.

Patients were followed up 7-10 days, 6 weeks, 3 and 6 months after the procedure. In the follow up visits, changes in the patients' well-being, blood tests outcomes, compliance with the diet instructions and weight were recorded. At 6 weeks, 3 and 6 months after the procedure, presence and location of the stiches by means of endoscopy, and quality of life were recorded.

Results - Eleven obese class I and II patients are included in this analysis.

The age range of the patients was 35-51 years, their average weight was 111.1 kg, their average height was 174 cm and their BMI (kg/m²) ranged from 30.2-39.7.

Thirty-one (31) procedures were applied in 11 patients. All procedures (100%; 95% CI [89%,100%]) were completed successfully.

All eleven patients reached 3-months and adhered until 6-month follow-up. The mean \pm SD TBWL at 3-month and 6-month was 14.8 ± 4.8 Kg and 17.8 ± 6.7 Kg, respectively (p<0.001). The mean \pm SD %TBWL at 3-month and 6-month was $13.5 \pm 4.7\%$ and $16.2 \pm 6.0\%$, and the mean \pm SD %EBWL was $46.5 \pm 28.6\%$ and $54.3 \pm 28.4\%$, respectively.

The mean \pm SD of waist circumference at baseline was 117 ± 9.4 and significantly (p<0.001) reduced 6 months after the EndoZip procedure to mean \pm SD of 100 ± 12.7 .

Safety evaluation - There were no adverse events related to the study. Two events unrelated to the device and / or EndoZip procedure occurred during the study.

7.0 Benefit - Risk Assessment

7.1 Potential Benefits

EndoZip™ System is an automatic, operator-friendly ESD that allows the user to create multiple internal gastric segmentation in the stomach by using an endoscopic approach. The System generates an endoluminal gastroplasty that restricts the stomach and impair motility. Since this is an endoluminal approach, the potential for leaks has been significantly minimized. Also, this procedure is reversible and requires short recovery duration, and thus may be applied to a much wider patient population, by gastroenterologists as well as surgeons.

NiTiNotes has performed several preclinical and clinical studies in the development process with prototypes of varying designs as with the final device configuration.

In a First In Human study including 11 patients and 31 suture procedures, the first EndoZip prototype device presented promising safety and effectiveness results of %TBWL of 16.2 ± 6.0 at 6 months. No SAE related to the study occurred within the study duration. In an extended feasibility study a technical failure occurred and study was early terminated. The final design configuration includes improvements aim to minimize the likelihood of such an event.

The following are potential benefits of the EndoZip™ System stratified by key stakeholders:

Physicians:

- An effective non-surgical, long lasting treatment.
- Facilitate reduction in comorbidities.
- User-friendly procedure that has a minimal learning curve and provides reproducible results (not operator-dependent).
- Can be readily available for in clinic use, thereby improving patient access.
- Lower risk profile while still providing clinically significant weight loss outcomes.
- Short procedure with potential of cost reduction.

	Title: Evaluation of EndoZip™ System (AS) in Obese Patients who failed to reduce weight with non-surgical weight-loss methods		
Document No: CL00003	Rev: 1.0	Page:	30 of 83

Patients:

- Favorable safety profile with minimal trauma.
- Effective non-surgical, long lasting treatment.
- Potentially easier and shorter recovery.

Healthcare System:

- Lower expenditure - Patients are expected shorter recovery and reduced complications
- Procedure can be conducted by endoscopists and surgeons

7.2 Anticipated Risks

The EndoZip system is an ESD, hence the complication associated with using it are anticipated to be similar to other endoscopic suturing devices such as OverStitch™ Endoscopic Suturing System (K181141). As with any intragastric suturing procedure, using the EndoZip System may lead to the following potential risks:

1. Severe tissue trauma that requires operation (e.g., perforation, obstruction, unscheduled implant removal due to severe pain or other symptoms, etc.).
2. Severe patient infection / biologic reaction that requires intensive care unit treatment.
3. User electric shock/injury hazard/Fire.
4. Moderate tissue trauma that requires therapy other than a surgical operation (e.g., ulcer, GI bleeding, GERD, etc.).
5. Minor patient infection / biologic reaction.
6. Minor user infection / biologic reaction.
7. Minor tissue trauma and/or patient discomfort that can be managed with prescription drugs and / or mild intervention (e.g., dehydration, cutaneous bleeding, laceration, esophagitis, gastritis, severe vomiting, etc.).
8. Extended procedure time.
9. Failed procedure.
10. Equipment damage to endoscope.

	Title: Evaluation of EndoZip™ System (AS) in Obese Patients who failed to reduce weight with non-surgical weight-loss methods		
Document No: CL00003	Rev: 1.0	Page:	31 of 83

11. Patient discomfort (e.g. nausea, vomiting, bloating, cramps, diarrhea, constipation, etc.).
12. User injury hazard.
13. User inconvenience.

All risks of using EndoZip were mitigated by design and verification tests. NitiNotes' risk management process complies EN ISO 14971:2019. The potential residual risk following the mitigations are all acceptable (for more details please refer to "Risk analysis report").

As described in the following section, the device's benefits outweigh these risks.

7.3 Benefit – Risk Assessment

The EndoZip™ System is expected to provide significant weight loss outcomes including responder rate, defined as $\geq 5\%$, of at least 50% at 12 months. In addition, the EndoZip™ System is a minimally invasive procedure, a reproducible and easy to use device that can aid the obesity treatment by expanding the access and acceptability to a broad population segment. The expected risks associated with the system use may require, at most, surgical or endoscopic intervention, thus safety profile meets the low to moderate risk. The EndoZip™ System is designed to minimize these risks. In addition, the company applied the relevant special control activities to ensure that the system performs in accordance with its performance specifications. Thus, it is reasonable to conclude that the device's benefits will outweigh its risks.

8.0 Study Objectives

8.1 Primary objectives

The evaluate the safety and effectiveness of the EndoZip system procedure, followed by lifestyle modifications, for weight reduction in obese patients with BMI of 30-40 kg/m².

8.2 Secondary objectives:

- To evaluate the potential improvement in patients' conditions.
- To evaluate the duration related to the EndoZip procedure.
- To evaluate physicians' satisfaction related to the EndoZip usability.

9.0 Study Endpoints

9.1 Primary endpoints

	Title: Evaluation of EndoZip™ System (AS) in Obese Patients who failed to reduce weight with non-surgical weight-loss methods	
Document No: CL00003	Rev: 1.0	Page: 32 of 83

The effectiveness of the EndoZip system will be assessed by the following co-primary endpoints:

1. Mean percent of total body weight loss (%TBWL) after 12 months.
2. Percentage of patients with a reduction in %TBWL of at least 5% at 12 months.

Safety will be characterized through a summary of the incidence of adverse events and serious adverse events by relation to study treatment.

A Data Safety Monitoring Board (DSMB) will review and adjudicate all serious device related and non-related adverse events and any other events deemed necessary.

9.2 Secondary endpoints

The following secondary endpoints will be evaluated:

1. Percent of excessive weight loss (%EWL) over 6 and 12 months.
2. Reduction of weight and waist circumference over 6 and 12 months.
3. Impact of EndoZip procedure on gastric motility at 6 months.
4. Changes in Weight-related Quality of Life (IWQOL) Questionnaire scores at 6 and 12 months.
5. Time analysis including procedure duration, anesthesia duration, patient recovery duration.
6. Change in comorbid conditions over 12 months evaluated by:
 - a. Blood pressure
 - b. Glucose, HbA1c
 - c. Lipid levels (Total Cholesterol, LDL-C, HDL-C, and triglycerides)
 - d. Sleep Apnea test
7. Physicians' satisfaction based on a questionnaire

10.0 Study Design

[figure not shown]
This multicenter, prospective, single arm study will include up to 45 patients (10-20 patients per site), aimed at evaluating the performance of the EndoZip System in obese patients who failed to reduce weight with non-surgical weight-loss methods.

The first two (2) patients in each site will be considered as run-in period, to compensate for any learning curve that may be required for the EndoZip performance evaluation.

Patients will be enrolled at up to 5 clinical sites in Europe and Israel. Patients who meet the eligibility criteria is expected to come the clinic for at least 10 visits.

	
Title: Evaluation of EndoZip™ System (AS) in Obese Patients who failed to reduce weight with non-surgical weight-loss methods
	
Document No: CL00003	Rev: 1.0	Page: 33 of 83

10.1 Study Flow Chart

11.0 Patient Selection and Enrollment

After being informed of the nature of the study, the patient will sign a written informed consent form (ICF) that has been approved by the appropriate Institutional Ethics Committee (IEC) and regional Competent Authority (CA). Enrollment of up to 45 patients is planned.

Patients will be considered for the study if they meet the specific inclusion/exclusion criteria. The criteria for enrollment must be followed explicitly.

	Title: Evaluation of EndoZip™ System (AS) in Obese Patients who failed to reduce weight with non-surgical weight-loss methods		
Document No: CL00003	Rev: 1.0	Page:	34 of 83

Enrollment completion is expected to take place up to 6 months following IEC approval of the study.

11.1 Inclusion Criteria

1. Age 21-70
2. BMI ≥ 30 and $\leq 40 \text{ kg/m}^2$
3. Willingness to comply with the substantial behavioral modifications program as required by the procedure
4. Patients with history of failure with non-surgical weight-loss methods
5. Willingness to follow protocol requirements, including signed informed consent, routine follow-up schedule, completing laboratory tests, completing IWQOL questionnaire and completing the medically supervised diet and behavior modification program
6. Residing within a reasonable distance from the investigator's office and able to travel to the investigator to complete all routine follow- up visits.
7. Ability to give informed consent
8. Women of childbearing potential (i.e., not post-menopausal or surgically sterilized) must agree to use adequate birth control methods

11.2 Exclusion Criteria

1. Prior surgery of any kind on the gastrointestinal tract (except uncomplicated cholecystectomy or appendectomy).
2. Patients with history of small bowel or colonic obstruction, and/or adhesive peritonitis and/or abdominal adhesions.
3. Patients with any inflammatory disease.
4. Patients with history of cancer in the gastrointestinal tract.
5. Potential upper gastrointestinal bleeding conditions such as a history of angioectasias.
6. A known gastric mass or gastric polyps $> 1 \text{ cm}$ in size.
7. Patients with TG > 500 or LDL > 190 .
8. A known hiatal hernia $> 4\text{cm}$ of axial displacement of the z-line above the diaphragm or severe or intractable gastro-esophageal reflux symptoms while on maximal medical therapy.
9. A structural abnormality in the esophagus or pharynx such as a stricture or diverticulum that could impede passage of the endoscope.
10. Patient with motility disorders of the GI tract or intractable constipation.
11. Patients with known coagulation disorder (INR > 1.5) or on anticoagulation therapy.
12. Type 1 diabetes or Type 2 diabetes with a HgbA1c > 8 in 6 weeks prior the procedure or use of any medication for diabetes other than metformin. Patients with any serious health condition unrelated to their weight that would increase the risk of endoscopy.

	Title: Evaluation of EndoZip™ System (AS) in Obese Patients who failed to reduce weight with non-surgical weight-loss methods		
Document No: CL00003	Rev: 1.0	Page:	35 of 83

13. Patients with chronic abdominal pain
14. Patients with hepatic insufficiency or cirrhosis
15. Patients that used an intragastric device for weight loss within 2 years prior to this study.
16. Patients with psychological health questionnaire-9 (PHQ-9) score of 10 or higher.
17. Patients receiving daily prescribed treatment with high dose aspirin (> 100mg daily), anti-inflammatory agents, anticoagulants or other gastric irritants.
18. Patients with history or current abuse of drugs or alcohol
19. Patients with known hypersensitivity to Spirulina, egg, milk or wheat allergens (unable to go through the GEBT)
20. Patients who are unable or unwilling to take prescribed proton pump inhibitor medication.
21. Patients who are pregnant or breast-feeding.
22. Patients who are taking medications that cause weight loss.
23. Patients with Severe cardiopulmonary disease or other serious organic disease which might include known history of coronary artery disease, Myocardial infarction within the past 12 months, poorly-controlled hypertension, required use of NSAIDs
24. Patients taking medications on specified hourly intervals that may be affected by changes to gastric emptying, such as anti-seizure or anti-arrhythmic medications.
25. Patients who are taking corticosteroids, immunosuppressants, and narcotics.
26. Symptomatic congestive heart failure, cardiac arrhythmia or unstable coronary artery disease.
27. Pre-existing respiratory disease such as chronic obstructive pulmonary disease (severe COPD), pneumonia or cancer.
28. Diagnosis of autoimmune connective tissue disorder (e.g. lupus, HIV, erythematosus, scleroderma) or immunocompromised
29. Specific diagnosed genetic disorder such as Prader Willi syndrome (motility disorder).
30. Eating disorders including night eating syndrome (NES), bulimia, binge eating disorder, or compulsive overeating.
31. Known history of endocrine disorders affecting weight such as uncontrolled hypothyroidism.

11.3 Withdrawal Criteria

Patients may withdraw from the study at their own request or at the request of their legally acceptable representative. The investigator may withdraw a patient from the study at any time for the following reasons:

- ❖ Severe side effects clearly related to the study device.
- ❖ Presence or appearance of exclusion criteria.
- ❖ Appearance of accompanying diseases rendering further participation in the study impossible.
- ❖ A significant protocol violation, as determined either by the sponsor or the investigator

	
Title: Evaluation of EndoZip™ System (AS) in Obese Patients who failed to reduce weight with non-surgical weight-loss methods
		
Document No: CL00003	Rev: 1.0	Page:	36 of 83

- ❖ Patient noncompliant with investigational procedures
- ❖ Patient noncompliant with visits
- ❖ At the specific reasonable request of the sponsor

The sponsor must be informed in each withdrawal case. The reason for withdrawal must be recorded in the eCRF and in the patient file.

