5.1.3 Study Rationale

NiTiNotes Ltd. has developed the EndoZip System which offers obesity treatment by an operator-friendly endoscopic procedure generating an endoluminal gastroplasty that restricts the stomach and impairs motility.

	Title: Evaluation of EndoZip™ System (AS) in Obese Patients who failed to reduce weight with non-surgical weight-loss methods		
Document No: CL00003	Rev: 1.0	Page:	24 of 83

The EndoZip system is designed to allow for the creation of multiple internal gastric segmentations in the stomach by using an endoscopic approach. The system allows the forming of wall-to-wall longitudinal attachments of the anterior and posterior stomach walls, creating multiple plications within. Another important determinant which predicts a favorable safety outcome is the minimally invasive nature of the procedure.

The pre-clinical studies and initial human study (details are provided in 6.2 and 6.3), using an earlier configuration of the device, have proven to have excellent safety profile, and provided initial performance data.

The aim of this study is to evaluate the updated device configuration of EndoZip system to establish the long-term safety and further validate the efficacy claim in the intended population.

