15.11 Adverse Event Recording and Reporting

Assessment of the occurrence of an AE will be based on changes in the patient's signs and symptoms. AEs will be monitored until a patient completes the study unless the Investigator determines the event is related to the investigational device, in which case they will be monitored until resolution if possible. Medical care will be provided, as defined in the informed consent, for any AE related to study participation. AEs will be collected on an AE eCRF and applicable source documentation.

The following should not be considered an AE:

- A condition requiring a preplanned procedure unless the condition worsened since screening
- A preexisting condition found as a result of screening, unless the condition has worsened since enrollment.

All AEs observed during the course of this study, regardless of severity or relationship to the investigational device will be recorded on the appropriate eCRF.

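### Section 11.3 lets a treated patient be withdrawn from the study for a device harm, and no section then requires new adverse events to be collected up to month 12

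*Combined protocol and SAP*

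**What the plan says.** Section 11.3 (Withdrawal Criteria) states: "The investigator may withdraw a patient from the study at any time for the following reasons". The list includes "Severe side effects clearly related to the study device" and "Presence or appearance of exclusion criteria". After a withdrawal it requires only that the sponsor is informed and that the reason is recorded.

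Some exclusion criteria in section 11.2 describe conditions that could arise after treatment:
- No. 8 includes "severe or intractable gastro-esophageal reflux symptoms while on maximal medical therapy".
- No. 10 reads "Patient with motility disorders of the GI tract or intractable constipation".
- No. 13 is chronic abdominal pain.

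Treatment takes place on one procedure day (section 13.3), with non-absorbable material (section 6.1). Long-term safety is a stated aim (section 5.1.3) and safety is part of the primary objective (section 8.1). It is reported as the incidence of adverse and serious adverse events (section 9.1) and tabulated as cumulative incidence by seriousness, severity, expectedness and relationship (section 14.5). The safety set in sections 14.1 and 14.2.1 is all enrolled patients.

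**The concern.** In a drug trial, a rule of this kind can stop exposure. Here, once the procedure is done, no course of study treatment remains to be stopped, so withdrawal mainly stops the collection of data. One ground is itself a safety outcome. The other can be met by a condition that the device might plausibly cause. Whether a patient continues to be observed can then depend on whether harm has already appeared, which makes the loss of follow-up informative for safety.

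At stake are late, separate events in these patients: a second event of another type, a serious event after a severe but non-serious one, or a finding at the 2- or 6-month endoscopy. The Data Safety Monitoring Board, which advises on continuation (section 15.12), would work from the same incomplete record. The 12-month weight would also be missing. Section 14.4 plans no imputation beyond the mixed model and gives no missing-data rule for the 5% responder proportion.

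**Working it through.** The plan states no event rate, withdrawal rate or safety precision, so there is no figure to reproduce. The check is first textual.

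**Does any section require collection of new events after withdrawal?**

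| Section | What it covers | New events after withdrawal? |
|---|---|---|
| 11.3 | Inform sponsor, record reason | No |
| 13.9 | Three contact attempts before loss to follow-up is declared | No |
| 13.10, footnote | Monitoring to the end of the study period; unresolved events followed | Not stated for withdrawn patients |
| 15.1 | Collection until the follow-up period is completed | Not stated for withdrawn patients |
| 15.11 | "AEs will be monitored until a patient completes the study unless the Investigator determines the event is related to the investigational device", in which case to resolution if possible | No: covers a known event |
| 15.12 | Events still open at study end followed | No: covers a known event |
| 18.5 | Duty to complete follow-up if the sponsor stops the study or an investigator leaves | No: a different situation |

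There is no early-termination visit, and nothing distinguishes leaving protocol procedures from ending data collection. The three rules on open events also differ. Section 15.11 stops at study completion unless the event is device-related, the footnote in 13.10 accepts two weeks of stabilisation for a non-serious event, and 15.12 asks for resolution.

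**Observation lost per patient.** Withdrawal at the 1-week visit loses about 51 of 52 weeks and both follow-up endoscopies. Withdrawal at 2 months loses 12 − 2 = 10 of 12 months.

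**Illustration of the effect. Every rate is an assumption.** Let h be the share of patients with an early device harm, w the share of those who are withdrawn, and r_h and r_o the risks of a new late harm with and without early harm.

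- True late-harm rate = h·r_h + (1 − h)·r_o
- Observed rate, all patients in the denominator = h·(1 − w)·r_h + (1 − h)·r_o
- Share missed = h·w·r_h / [h·r_h + (1 − h)·r_o]

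Central case: h = 10%, r_h = 20%, r_o = 2%, w = 100%.

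- True: 0.10 × 0.20 + 0.90 × 0.02 = 3.8%
- Observed: 0.90 × 0.02 = 1.8%
- Missed: 0.020 / 0.038 = 53%
- Chance of seeing at least one late event in 45 patients: 1 − 0.962^45 = 0.83 with full follow-up, 1 − 0.982^45 = 0.56 with withdrawal

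| h | r_h | w | Share missed |
|---|---|---|---|
| 5% | 10% | 100% | 0.005 / 0.024 = 21% |
| 10% | 20% | 50% | 0.010 / 0.038 = 26% |
| 10% | 20% | 100% | 53% |
| 20% | 40% | 100% | 0.080 / 0.096 = 83% |
| 5–20% | 2% (no excess risk) | 100% | 5–20% |
| any | any | 0% | 0% |

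**The case against.** The strongest reply is that section 11.3 grants a permission and imposes no duty, and that other sections already follow the event that matters. Both parts are true. An investigator may keep the patient, and the event that prompts withdrawal is recorded and followed. In the only completed study, all 11 patients stayed to 6 months with no related events (section 6.3), although its extension had one serious event (section 6.3.1). What remains is the gap for new events, and discretion leaves it open: at up to five sites, the same harm could be followed at one and not at another.

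Stronger readings are tempting, and the documents do not support them:

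- **That the intended effect triggers withdrawal.** The device is described as "generating an endoluminal gastroplasty that restricts the stomach and impairs motility", and criterion 10 names motility disorders. No section says that slower emptying on the breath test counts as such a disorder. The test is scheduled for all patients at 6 months and serves a secondary endpoint (section 9.2), which points the other way.
- **That many exclusion criteria restate the risks in section 7.2.** Nos. 1, 2 and 5 are worded as prior surgery, past obstruction or predisposing conditions at entry. The overlap with nos. 8, 10 and 13 is plausible but inexact. For example, 7.2 lists reflux disease under moderate trauma, while no. 8 requires severe or intractable symptoms on maximal therapy.
- **That adverse event incidence as a whole is biased low.** A patient withdrawn for a device-related event is already counted among patients with any device-related event. Later events do not change that proportion.
- **That exposure always continues.** The material is non-absorbable, but section 7.1 calls the procedure reversible and 7.2 mentions unscheduled removal.
- **That these patients are the most likely to have late harm.** This is plausible, but no figure in the documents supports it.

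**Conclusion.** The point holds in a limited form. Section 11.3 permits withdrawal of a treated patient from the study because of a device harm, or because an exclusion criterion has appeared. Nothing in the protocol requires new events to be sought in that patient afterwards. Event counts, specific event types (including the major complications to be reported under section 15.11.1) and later serious events can be under-reported while the patient remains in the denominator.

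The effect cannot be sized from the documents. The 21–83% range depends on assumed rates and on every early-harmed patient being withdrawn. It falls in proportion to the share actually withdrawn and is zero if safety follow-up continues. The textual gap does not depend on those assumptions.

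**What to change.** In section 11.3, separate leaving protocol procedures from ending data collection. State that for a treated patient only withdrawal of consent or loss to follow-up ends data collection. A patient who meets any other ground stays in collection of adverse events, serious adverse events and device deficiencies to month 12, and of weight where the patient attends, with a status flag in the eCRF.

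Use the contacts already planned. After month 2 these are five in-person visits (4, 6, 8, 10 and 12 months) and five calls (3, 5, 7, 9 and 11 months). Section 13.9 describes the calls as counselling, so an adverse event question would have to be added to them.

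The sponsor should also state whether the appearance of exclusion criteria is a ground after the procedure. That statement should be reconciled with the 6-month motility endpoint (9.2) and with the follow-up text in 13.10, 15.1, 15.11 and 15.12. Which examinations and what care such a patient receives stays with the investigator.

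The cost is protocol wording, one eCRF field and a few contacts that would otherwise lapse. The reported adverse event rate may be slightly higher.
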